11 SERUM NICOTINE ANALYSIS

11.1 Participation in Serum Nicotine Analysis

A blood sample collected for the analysis of serum nicotine levels will be used to confirm that patients meet eligibility and screening criteria. Blood samples will also be collected once during Cycle 1, once at the beginning of Cycle 2 before nicotine transdermal patch administration, once during Cycle 2, and once during the 30-day follow-up period to measure serum nicotine levels throughout the study (a total of 5 blood samples). Participation in serum nicotine studies using blood samples is mandatory.

11.2 Collection, Processing, and Distribution of Samples

The study team will coordinate collection and de-identification of all blood samples.

11.2.1 Collection Time Points

Blood samples will be collected at the following time points:

- Eligibility/Baseline (during eligibility screening)
- Cycle 1, Treatment Condition 1, Day 8 or within 5 days
- Cycle 2, Treatment Condition 2, before nicotine transdermal patch administration
- Cycle 2, Treatment Condition 2, Day 8 or within 5 days
- 30-day follow-up period, Day 8-15 or within 7 days

11.2.2 Blood Sample Collection Instructions

At least 2.0 mL of blood will be collected at each of the time points listed in Section [11.2.1](#). Blood collection will follow VCU Toxicology Laboratory specimen specifications.

11.2.3 Labeling for all Blood Samples

- Study number
- Patient study identification number
- Date of sample collection
- Time of sample collection
- Study time point

11.2.4 Tracking for all Blood Samples

Collection and distribution of all blood samples will be logged by the study team in OnCore.

12 STUDY CALENDAR

Table 3. Study Caledar – Eligibility/Screening Through Washout Period

	Eligibility and Screening	Cycle 1 Treatment Condition 1 7mg Nicotine Transdermal Patch ^A			Washout Period No Nicotine Transdermal Patch ^B
	Within 14 Days	D1	D2	D8 ^C	
Informed Consent ^D	X				
Demographics	X				
Vital Signs (BP, HR) ^E	X	X		X	
Baseline Conditions/Symptoms	X				
Medical/Surgical History	X				
Exam ^F	X ^G			X	
Concurrent Medications ^H	X	X		X	
Urine Pregnancy Test	X				
Serum Nicotine Level	X			X	
Assessment of AEs		X		X	
BPI-SF	X			X	
QLQ-CIPN 20	X			X	
PGIC Neuropathy (upper and lower)				X	
AE Assessment Phone Call			X		X ^I

Table 3 Footnotes:

- A. Each Treatment Condition Cycle is 14 days.
- B. Washout period may occur for \geq 14 days and up to 21 days after the removal of the nicotine transdermal patch on Cycle 1
- C. Cycle 1, Day 8 study visit may occur within 5 days.
- D. If registration is delayed to more than 14 days after the informed consent form is signed, a new signed consent form is not required unless the IRB has approved a newer version.
- E. Include ECOG performance status.
- F. Exam will also include a neurological exam: sensory, motor, reflex, Romberg, and gait.
- G. If the neurological exam cannot be completed on the day of screening, it can be completed on Cycle 1, Day 1, but does not need to be completed for both screening and Cycle, Day 1.
- H. Include over-the-counter medications.
- I. The AE assessment phone call during the washout period will include notation of the date the last nicotine transdermal patch was removed in Cycle 1.

Table 4. Study Calendar – Treatment Condition 2 Through the 90-Day Follow-up Period

	Cycle 2 Treatment Condition 2 14mg Nicotine Transdermal Patch ⁰			30-Day Follow-up Period		90-Day Follow-up Period ^B
	D1 ^C	D2	D8 ^D	D1	D8 - D15 ^E	
Vital Signs (BP, HR) ^F	X		X		X	
Exam ^G	X		X		X	
Concurrent Medications ^H	X		X		X	
Serum Nicotine Level	X ^I		X		X	
Assessment of AEs	X ^I		X		X	
BPI-SF	X ^I		X		X	
PGIC Neuropathy (upper and lower)	X ^I		X		X	
QLQ-CIPN 20	X ^I		X		X	
AE Assessment Phone Call		X		X ^J		
Follow-up Phone Call						X ^{B, K}

Table 4 Footnotes:

- A. Each Treatment Condition Cycle is 14 days.
- B. The 90-day follow-up period will begin at the end of Cycle 2, after the last nicotine transdermal patch is removed. The 90-day follow-up phone call may occur \pm 14 days.
- C. Cycle 2, Day 1 may occur \geq 14 days and up to 21 days after the removal of the nicotine transdermal patch in Cycle 1.
- D. Cycle 2, Day 8 study visit may occur within 5 days.
- E. 30-day follow-up, Day 8 - Day 15 study visit may occur within 7 days.
- F. Include ECOG performance status.
- G. Exam will also include a neurological exam: sensory, motor, reflex, Romberg, and gait.
- H. Include over-the-counter medications.
- I. Must occur before 14 mg nicotine transdermal patch is administered.
- J. 30-day follow-up, the AE assessment phone call will include notation of the date the last nicotine transdermal patch was removed in Cycle 2.
- K. 90-day follow-up, the phone call will assess whether patients have continued to use the nicotine transdermal patch to lessen their CIPN symptoms and if they have developed a dependence to nicotine in any form (eg, cigarettes, electronic cigarettes, smokeless tobacco, or other nicotine-containing products).

13 STATISTICAL CONSIDERATIONS

13.1 Study Design

This is a phase 2 study that will test the efficacy of acute nicotine transdermal patch administration using an open-label, crossover within-subjects clinical trial design with nicotine transdermal patch concentrations of 7 mg and 14 mg. Patients will be evaluated for nicotine-associated toxicity and undergo assessments of pain and neuropathy administered by the study team, which will provide subjective and clinical measurements at baseline, during treatment conditions, and post-treatment. The primary endpoint is to assess the efficacy of short-term nicotine transdermal patch administration in the treatment of CIPN in patients whose cancer is stable or in remission by assessing decreases in neuropathic pain symptoms measured by the total sensory score of the EORTC QLQ-CIPN-20.

13.1 Sample Size and Accrual

Using the 19-76 numerical scale for QLQ-CIPN220, a minimum decrease of 2.7 points (range of 2.7 – 5.6 points) would be required to improve the patient's quality of life by one grade (grade 2 to grade 1). A sample size of 47 would provide a power of at least 95% to detect a minimum change of 2.7 EORTC QLQ-CIPN20 scale points, assuming a moderately sized effect (ie, effect size 0.54) and 5% level of significance. Assuming 10% dropout or non-compliance, this will bring the total size to 52 patients. Recruitment ends when the required number of evaluable patients to complete the study is reached. A patient is evaluable if pain scores are available for the patient with each dose level. This still might have missing values due to non-compliance. All of the patients will be included in the final analysis and subjects with missing values will be included based on imputation-based method provided the amount of missing values is not excessive. If final data contains patients with more than 50% missing observations, we will use a pattern mixture model for imputation of missing data followed by longitudinal data.

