13.2 Statistical Analysis

13.2.1 Analysis of Primary Endpoint

The primary endpoint of the study is the decrease in neuropathic pain symptoms for CIPN patients using a short-term nicotine transdermal patch. CIPN PROs will be measured using the EORTC QLQ-CIPN20 sensory subscale score. The QLQ-CIPN20 numerical score has a range of 19-76, in which lower scores indicate less symptoms and a better quality of life. Patient QLQ-CIPN20 scores at baseline, during treatments, and post-treatment will be analyzed by a one-sided test of the hypothesis using a matched paired t-test using 5% level of significance. Data will be tested for compliance with normality assumption and simple transformations would be used if required to restore normality of the data.

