13.4.2 Efficacy Evaluability

All blood samples collected for an individual patient will need to be analyzed for serum nicotine levels to determine if an individual patient is evaluable for efficacy. A nicotine serum value of > 2.0 ng/mL and a cotinine serum value of > 2.0-20 ng/mL via LC-MS/MS analysis is consistent with the use of nicotine. A nicotine or cotinine serum value of > 10-20 ng/mL via immunoassay analysis is consistent with the use of nicotine. Evaluability may not be determined until the patient has completed the study treatment and is off study and serum nicotine analysis has been for all blood samples.

A patient is evaluable for efficacy if **ALL** of the following study requirements have been fulfilled:

- Attended at least 60% of the visits (≥ 3 out of 5 visits).
- Maintained a therapeutic level of serum nicotine for at least 60% of the serum nicotine analysis time points (≥ 3 out of 5 blood samples).
- Completed at least 60% of the survey/questionnaire data collection points (≥ 3 out of 5 data collection points; and 2 out of 4 for the PGIC). Each data collection point will include an EORTC QLQ-CIPN-20 questionnaire and BPI-SF questionnaire. The neuropathy upper and lower extremity PGIC questionnaires will only be collected at 4 points throughout the study.

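### Sections 13.1, 13.2.1 and 13.4.2 do not agree on who is in the primary analysis, how missing scores are handled, or which analysis follows

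*Combined protocol and SAP*

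**What the plan says.** The relevant rules stand in three places of the combined protocol and SAP.

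- **Section 13.1, Sample Size and Accrual** (the number 13.1 is used twice). On the analysis set: "All of the patients will be included in the final analysis and subjects with missing values will be included based on imputation-based method", on the condition "provided the amount of missing values is not excessive". No number is given for that condition and the method is not named. A second rule follows: "If final data contains patients with more than 50% missing observations, we will use a pattern mixture model for imputation of missing data". That sentence closes with "pattern mixture model for imputation of missing data followed by longitudinal data" and stops there. The same paragraph has its own evaluability rule: "A patient is evaluable if pain scores are available for the patient with each dose level".
- **Section 13.2.1.** "Patient QLQ-CIPN20 scores at baseline, during treatments, and post-treatment will be analyzed by a one-sided test of the hypothesis", by a matched paired t-test at the 5% level. It names no analysis set, does not mention missing data, and does not say which scores form the pair.
- **Section 13.4.2.** Efficacy evaluability has three conditions, all of which must be met. One is "Completed at least 60% of the survey/questionnaire data collection points", given as at least 3 of 5. The others are attendance at 3 of 5 visits and a therapeutic serum nicotine level in 3 of 5 samples.

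**The concern.** The threshold that calls for the pattern mixture model and the threshold for efficacy evaluability divide patients at the same point. A patient sparse enough to trigger the model is one whom Section 13.4.2 does not count as evaluable for efficacy, yet Section 13.1 keeps that patient in the final analysis. The link from imputation to the primary test is also missing: Section 13.1 points to something longitudinal, and Section 13.2.1 to a paired t-test.

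This matters because the patients affected may not be a random subset. Section 7.2.2 requires discontinuation for qualifying toxicities, and Section 6.2.1 fixes the order of the two patch strengths. Someone who stops in Cycle 1 and attends no later visit has few scores. In an open-label, single-arm trial with a within-patient test, whether such patients count, and how, should not be open at the time of analysis.

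**Working it through.** **Inputs.** Five QLQ-CIPN20 time points: screening, Cycle 1 Day 8, Cycle 2 Day 1 before the patch, Cycle 2 Day 8, and follow-up (Section 12, Tables 3 and 4). BPI-SF is on the same schedule. The screening score is always present, because Section 4.1.2.2 requires it for entry. Sample size 47, effect size 0.54, 5% level, 52 after a 10% allowance (Section 13.1).

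**The plan's own figure.** For a paired t-test with 46 degrees of freedom and noncentrality 0.54 × √47, power is 95.2% two-sided and 97.7% one-sided, so the stated 95% is reproduced. 47 × 1.10 = 51.7, which gives 52. The sample size is not in dispute.

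**Overlap of the two thresholds.** 50% of 5 is 2.5, so more than 50% missing means at least 3 missing and at most 2 completed. Of the 32 present/missing patterns, 1 + 5 + 10 = 16 have at most 2 completed, and none of these has 3 or more. Only 1 of the 16 contains both on-patch scores, and it lacks the screening score that entry requires. So, if pain scores are collected together with QLQ-CIPN20, no enrolled patient over the 50% line is evaluable under Section 13.1's rule either.

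For patients who leave and attend no later visit:

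| Last score | Completed | Missing | Handling in 13.1 | Evaluable by 13.1 rule | 13.4.2 questionnaire condition |
|---|---|---|---|---|---|
| Screening | 1 | 80% | pattern mixture | no | not met |
| Cycle 1 Day 8 | 2 | 60% | pattern mixture | no | not met |
| Cycle 2 Day 1 | 3 | 40% | unnamed imputation | no | met |
| Cycle 2 Day 8 | 4 | 20% | unnamed imputation | yes | met |

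The statement that all patients are analysed covers all four rows; the two evaluability rules differ from it and, in the third row, from each other.

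**Size if imputed values were treated as observed.** This is an illustration: the documents name no method. Assume N = 52 change scores, m missing at random, k = N − m observed. With mean imputation the estimate is unchanged, but the naive standard error divided by the true one is √[k(k−1) / (N(N−1))].

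- m = 5: √(47 × 46 / (52 × 51)) = √(2162/2652) = 0.90
- m = 10: √(42 × 41 / (52 × 51)) = √(1722/2652) = 0.81

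The one-sided type I error is P(t with k−1 df > ratio × 95th percentile of t with 51 df). Single random-draw imputation was simulated for comparison.

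| Imputed of 52 | Type I error, random draw to mean imputation |
|---|---|
| 1 | 5.3% to 5.4% (mean imputation is the lower here) |
| 3 | 5.9% to 6.1% |
| 5 | 6.7% to 6.9% |
| 10 | 8.5% to 9.2% |
| 16 | 10.8% to 12.8% |

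Multiple imputation (20 imputations) with Rubin's rules stayed at 4.6% to 5.0% in all five cases.

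**The 13.4.2 set.** Section 11.2.1 lists five blood samples. Only Cycle 1 Day 8 and Cycle 2 Day 8 are scheduled on patch, against a requirement of therapeutic levels in at least 3 of 5. Read literally, the efficacy-evaluable set could be nearly empty.

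**The case against.** The best defence is that there is no conflict. Section 13.4.2 defines who is evaluable but never says that others leave the primary analysis, and in Section 13.1 evaluability governs when recruitment ends. The inclusion of all patients would then settle the matter, with a 50% threshold stated in advance. This has some force: the documents do not declare two primary populations. But Section 13.2.1 names no set, a rule headed efficacy evaluability would ordinarily be taken to define an efficacy analysis, and no text says otherwise.

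A reader might also infer more than the documents support:

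- **That pattern mixture scores are fed into the paired t-test.** No section says so. The reference to longitudinal data, although incomplete, points elsewhere.
- **That the pattern mixture model applies only to non-evaluable patients.** The sentence can equally mean that the presence of such patients switches the method for the whole dataset.
- **That the standard errors will be too small.** This needs single imputation treated as real data. Proper multiple imputation is not excluded.
- **That about 5 of 52 patients will pass the 50% line.** The 10% allowance covers dropout or non-compliance. A non-compliant patient may have every score, and one who leaves after Cycle 2 Day 1 already has 3 of 5.
- **That exclusion favours the patch.** No document links tolerability to the sensory score.

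Finally, the non-overlap is exact only if observations are counted as questionnaire time points. Counted by item or across all variables, it need not be.

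**Conclusion.** The point holds as a disagreement between sections on the analysis set, the imputation method and the analysis that follows. Counted by questionnaire, the 50% trigger and the 3-of-5 rule are exact complements, so whether an early leaver contributes to the primary result depends on the section followed. Bias from leaving such patients out is plausible but not shown, and its direction is not established.

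The effect on error rates is conditional. With 5 of 52 change scores mean-imputed and treated as observed, the standard error would be about 10% too small and the one-sided type I error about 7% instead of 5%. These figures assume missingness at random and a method that the plan does not name. They show what the unspecified step could cost, not what the plan will do. The change should be made before the data are analysed.

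**What to change.** 1. Name all treated patients as the primary analysis set in Section 13.2.1.
2. Replace the unnamed imputation and the 50% switch with a linear mixed model on all available QLQ-CIPN20 sensory scores, with visit as a fixed effect and an unstructured covariance.
3. Name one contrast in advance. The sponsor should choose it to match its stated endpoint; Section 13.2.1 lists baseline, during-treatment and post-treatment scores without saying which are compared. With complete data, a contrast between two visits gives the same estimate and standard error as the paired t-test, so the sample size argument carries over.
4. Keep the pattern mixture model as a sensitivity analysis only, by multiple imputation with Rubin's rules and with the assumption about unobserved scores stated in advance.
5. Use the Section 13.4.2 set for a supportive analysis only, after reconciling its serum nicotine condition with the sampling schedule and its evaluability rule with the one in Section 13.1.

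The cost is SAP wording and somewhat more analysis work. No new data or patients are needed. The downside is that the primary model assumes missing at random, which the sensitivity analysis examines. Naming one analysis set and specifying proper multiple imputation would also close the gap; the mixed model is preferred because it uses every available score without an imputation step in the primary analysis.

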13.2 Statistical Analysis

13.2.1 Analysis of Primary Endpoint

The primary endpoint of the study is the decrease in neuropathic pain symptoms for CIPN patients using a short-term nicotine transdermal patch. CIPN PROs will be measured using the EORTC QLQ-CIPN20 sensory subscale score. The QLQ-CIPN20 numerical score has a range of 19-76, in which lower scores indicate less symptoms and a better quality of life. Patient QLQ-CIPN20 scores at baseline, during treatments, and post-treatment will be analyzed by a one-sided test of the hypothesis using a matched paired t-test using 5% level of significance. Data will be tested for compliance with normality assumption and simple transformations would be used if required to restore normality of the data.

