3.2 Primary Endpoint

Efficacy of short-term nicotine transdermal patch administration in the treatment of CIPN in patients whose cancer is stable or in remission as defined by a ≥ 2.7 point decrease in the total sensory score of the EORTC QLQ-CIPN-20 (eg, an improvement in the patients quality of life by one grade).

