4.1.2 CIPN characteristics

4.1.2.1 Clinically diagnosed peripheral sensory neuropathy defined as:

4.1.2.1.1 Greater than Grade 1 peripheral sensory neuropathy using the CTCAE v5.0 grading scale

- **Grade 1** Asymptomatic
- **Grade 2** Moderate symptoms; limiting instrumental activities of daily living (ADL)
- **Grade 3** Severe symptoms; limiting self-care ADL
- **Grade 4** Life-threatening consequences; urgent intervention indicated

AND

4.1.2.2 Have a baseline CIPN PRO total sensory score ≥ 24.3 on a 19 to 76 scale using the EORTC QLQ-CIPN-20 questionnaire

AND

4.1.2.3 Have a CIPN-related neuropathic pain score ≥ 4 on a 0 to 10 scale using the Brief Pain Inventory-Short Form (BPI-SF) item 5

Note: Patients currently being treated for CIPN will not be excluded and are allowed to continue their treatment and current treatment dose while on study.

4.1.3 Will not have used any nicotine or tobacco products (eg, cigarettes, electronic cigarettes, smokeless tobacco, or other nicotine replacement therapies) within 14 days prior to study treatment start date

4.1.4 Eastern Cooperative Oncology Group (ECOG) performance status of 0, 1, or 2 (see [Appendix 1](#))

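### The normality pre-test with unnamed transformations in section 13.2.1 leaves the scale of the primary test to be chosen from the data and can take it off the 2.7-point scale that defines efficacy

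*Combined protocol and SAP*

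**What the plan says.** Section 13.2.1 analyses QLQ-CIPN20 scores at baseline, during treatment and after treatment by a "one-sided test of the hypothesis using a matched paired t-test using 5% level of significance". The next sentence adds the conditional step: "Data will be tested for compliance with normality assumption and simple transformations would be used if required to restore normality of the data". No normality test, significance threshold, tested variable, list of transformations, order of choice or fallback is named there or elsewhere.

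Three other places fix the scale in points:

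- Section 3.2 defines efficacy "as defined by a ≥ 2.7 point decrease in the total sensory score of the EORTC QLQ-CIPN-20".
- Section 13.1 (Sample Size and Accrual) says that "A sample size of 47 would provide a power of at least 95% to detect a minimum change of 2.7 EORTC QLQ-CIPN20 scale points". It gives 0.54 as the standardised effect behind this figure.
- Section 4.1.2.2 makes entry depend on the same score: "Have a baseline CIPN PRO total sensory score ≥ 24.3 on a 19 to 76 scale".

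**The concern.** A matched paired t-test assumes approximate normality of the within-patient differences, not of the scores at each visit, and with 47 pairs it tolerates moderate departures. The plan's wording allows the scores to be tested. Baseline scores are truncated from below by eligibility, so they can fail a normality test for a reason that has nothing to do with the validity of the t-test.

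The practical remedy also pushes towards the scores. Paired differences take both signs, and a log or square root is not defined for negative values, so the usual simple transformations would have to be applied to the scores.

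Two things are at stake. First, a test on transformed scores no longer concerns a mean change in points, which is the unit of both the efficacy definition and the sample size. Second, the scale of the single primary test would be settled after the data are seen, in an open-label trial, with several candidate transformations left open.

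**Working it through.** **1. The plan's own figure.** Inputs from section 13.1: 2.7 points, effect size 0.54, 5% level, 47 patients. Implied SD of the paired change = 2.7/0.54 = 5.0 points. Exact noncentral-t power for a paired test at d = 0.54 and n = 47 is 95.2% two-sided, and 47 is the smallest n that reaches 95%. One-sided, as section 13.2.1 plans, power is 97.7% and 39 patients would reach 95%. Both satisfy the stated claim. The calculation is on the untransformed point scale.

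**2. What a log transformation does to 2.7 points.** At a score of 24.3, a fall of 2.7 gives 21.6, a ratio of 21.6/24.3 = 0.889, or a fall of 11.1%. The same log change at the other Table 2 scores is:

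- at 29.9: 29.9 × 0.111 = 3.3 points
- at 33.6: 33.6 × 0.111 = 3.7 points

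Conversely, 2.7 points is 9.0% of 29.9 and 8.0% of 33.6. No single log change corresponds to the 2.7-point criterion, and the effect size of 0.54 does not carry over.

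**3. How often the cut-off triggers the rule.** Assumptions: baseline scores normal before truncation at 24.3, change SD 5.0, n = 47, Shapiro-Wilk at 5%, log if it rejects, zero mean change in points. The documents give no between-patient SD and no correlation between visits, so the means and SDs below are assumed. The means are taken from Table 2. With 3,000 trials the simulation error at 5% is √(0.05 × 0.95/3000) = 0.4 percentage points.

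| Mean, SD before truncation | Baseline scores rejected | False positives, test baseline then log (slope of change on baseline) |
|---|---|---|
| 33.6, 5 | about 8% | 5–6% |
| 33.6, 8 | about 34% | 6.8% (0), 5.2% (−0.3), 4.3% (−0.5) |
| 29.9, 8 | about 65% | 8–9% (0), 5.3% (−0.3), 3.7% (−0.5) |
| 24.3, 8 (extreme: mean at the cut-off) | about 90% | 10.4% (0) |

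Without truncation, baseline is rejected in about 4% of trials. The paired differences are rejected in about 4–7%. The untransformed test gives 4.2–5.1% false positives at slope 0. If the rule tests the differences instead, the log rule gives 4.5–5.4%.

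**4. Why the error rate moves, and in which direction.** With zero mean change in points, the mean log change is approximately −[Var(on treatment) − Var(baseline)]/(2m²), where m is the mean score. For total change variance 25 and slope b, the variance difference is 25 + 2b·Var(baseline). Take the 29.9/SD 8 case: after truncation m = 33.2 and SD = 5.9, so the variance is 34.8. The standard error of the mean log change is about 5/(33.2 × √47) = 0.022. The one-sided critical value with 46 df is 1.68.

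- b = 0: 25/(2 × 33.2²) = 0.0113, which is 0.52 standard errors. The rate is 1 − Φ(1.68 − 0.52), about 12%, against 10–11% simulated when the log is always used. With the log used in about 64% of trials: 0.64 × 10.3 + 0.36 × 5 = 8.4%.
- b = −0.3: (25 − 20.9)/(2 × 33.2²) = 0.0019, or 0.09 standard errors; about 5.6%.
- b = −0.5: (25 − 34.8)/(2 × 33.2²) = −0.0044, or −0.20 standard errors; about 3%, that is, against nicotine.

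The sign changes at b = −25/(2 × 34.8) = −0.36. So the inflation requires on-treatment scores to be more spread out than the truncated baseline. With equal spread, or the same distribution at both visits, the log rule gives 4.1–5.7%.

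**5. Free choice.** If the most favourable of the raw, square-root, log and reciprocal results is taken once baseline fails the pre-test, the slope-0 scenarios give 9.7–20.5%. The plan's unnamed plural does not exclude such a choice, but does not state it either.

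**The case against.** The strongest reply is that the sentence directly follows the naming of a paired t-test, so the assumption it mentions is naturally that test's own: normal differences. On that reading the error rate stays at about 5%. This stands as a possible reading, but the text does not say so, and the object named in the section is the scores.

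A second reply is that 2.7 points is not the null value of the planned test, and a transformed p-value does not stop anyone from reporting the raw mean change. This is correct, so it would be too strong to say that no comparison with 2.7 remains possible. What remains is that the p-value and the estimate in points would then answer different questions.

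A third reply is that regression to the mean matters more. Under the study calendar the only QLQ-CIPN20 score before Cycle 1 is the screening score used for selection. In simulations with that feature and no treatment effect, the untransformed test rejects in 12–24% of trials and the pre-test with log in 13–27%. Most of that excess does not come from the transformation. This stands, and it limits what the present fix can deliver.

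A reader might infer that the rule roughly doubles the false-positive rate in favour of nicotine. The documents do not support that as a general statement. It needs scores rather than differences to be tested, a log or stronger transformation, and wider spread on treatment than at baseline. The documents fix none of these, and some plausible slopes put the rate below 5%. Nor does the scale floor of 19 explain skewed baseline scores, since nobody enters below 24.3.

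**Conclusion.** The concern holds as a defect of specification. From the documents alone: the rule is data-driven, its components are unnamed, it governs the primary test of an open-label trial, and a transformation of the scores would separate that test from the point scale of sections 3.2 and 13.1.

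Conditional on the scores being tested, the entry cut-off alone triggers the rule in about 8–65% of trials for baseline means of 29.9 or 33.6, and more often if the mean lies at the cut-off. The error rate relative to zero mean change in points is then about 4–10% for a single log rule, higher with a free choice among transformations, and about 5% if differences are tested or the spreads are equal. A log test may hold 5% for its own null of no mean log change; the discrepancy arises because the protocol's null is in points.

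All simulated figures rest on assumed baseline means, SDs and slopes, on Shapiro-Wilk at 5%, and on the log as the transformation. The change is worth making, but the trial's error rate has not been shown to be lost.

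**What to change.** Replace the sentence on normality in section 13.2.1 with:

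> The primary test is the paired t-test on untransformed within-patient point differences, reported as mean change in points with its confidence interval. The distribution of the differences will be inspected. A Wilcoxon signed-rank test (or bootstrap interval; name one) will be reported as a fixed sensitivity analysis that does not replace the primary test.

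This keeps the result in the unit of the 2.7-point criterion and keeps the planned power (97.7% one-sided at 47 patients if the change SD is 5.0). It needs no additional patients, visits or data. It does not address regression to the mean from using the screening score as baseline, which needs separate treatment.
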